2. BACKGROUND AND RATIONALE

2.1 Background on Condition, Disease, or Other Primary Study Focus

The COVID-19 global pandemic, caused by SARS-CoV-2 virus, represents a public health emergency with severe societal and economic impacts. Evaluating the potential for antiviral mouthrinses to inactivate SARS-CoV2 holds great potential for quelling the virus' spread among healthcare workers, who comprise up to 10% of COVID-19 cases.^{1,2} Healthcare providers like dentists, who deliver care in and near the oropharynx, suffer the highest risk of occupational

exposure.³ This is because SARS-CoV-2 is transmitted primarily through aerosol and respiratory droplets and salivary glands are a site of early SARS-CoV-2 viral replication and transmission.^{4,5} Dentists work in close proximity to the mouth and nasal passages with many procedures producing salivary airborne particles, particularly those involving ultrasonic and rotary instruments (hand pieces, “drills”) and 3-way syringes.⁵⁻⁸ High rates of SARS-CoV-2 transmission suggest that the minimum infectious dose is low compared to other viral diseases, and recent data suggest even one viral particle may be sufficient for infection.⁹ Working in close proximity to the oropharynx and generating salivary aerosols increases viral load exposure and therefore the risk of infection among dentists, oral surgeons, and other interventional doctors of the face.⁹ Furthermore, the proclivity of aerosols to remain airborne for up to 3 hours puts other patients, providers and staff at risk of exposure during aerosol-generating procedures, particularly in open bay clinics common to dental schools and large practices.^{4-6,10}

One promising strategy to reduce clinical spread is use of antiviral mouthrinses to inactivate SARS-CoV-2 infectability in saliva. Several commercially available mouthrinses have promising *in vitro* data with SARS-CoV-2 and *in vivo* data with other enveloped viruses, with a proposed mechanism of membrane disruption.^{3,11} Ethanol and Povidone-Iodine (PVP) solutions have been shown to reduce SARS-CoV-2 viral infectivity levels and titers *in vitro*.¹²⁻¹⁵ Cetylpyridinium chloride has promising *in vitro* data for inactivating SARS-CoV-2 infectivity.¹⁶ Chlorhexidine Gluconate (0.12%) has been widely adopted by practices with variable antiviral *in vitro* data.^{3,11} Finally, hydrogen peroxide mouthrinse (e.g. 1.5% w/v H₂O₂) is a widely available oral antiseptic capable of hydroxylating membranes, and is the a preprocedural mouthrinse recommended by the ADA to prevent transmission.¹⁷ No *in vivo* clinical data regarding SARS-CoV-2 exists to-date for most oral rinses including H₂O₂ mouthrinses.

Despite promising *in vitro* data, there is a dearth of *in vivo* clinical trials interrogating the efficacy of mouthrinses on reducing salivary SARS-CoV-2 viral infectivity. Given the rapid transmission and widespread distribution of the COVID-19 pandemic, the development of protocols and treatments mitigating transmission represent a major and urgent unmet public health need; this study will rigorously address the *in vivo* utility of widely available oral rinses in limiting SARS-CoV-2 viral infectivity and their acceptability in the dental healthcare setting.⁵⁻⁸

2.2 Study Rationale

One promising strategy to reduce clinical spread is use of antiviral mouthrinses to inactivate SARS-CoV-2 infectability in saliva. Several commercially available mouthrinses have promising *in vitro* data with SARS-CoV-2 and *in vivo* data with other enveloped viruses, with a proposed mechanism of membrane disruption.^{3,11-17} No *in vivo* clinical data regarding SARS-CoV-2 exists to-date for most oral rinses including H₂O₂ mouthrinses.

Despite promising *in vitro* data, there is a dearth of *in vivo* clinical trials interrogating the efficacy of mouthrinses on reducing salivary SARS-CoV-2 viral infectivity. Given the rapid transmission and widespread distribution of the COVID-19 pandemic, the development of protocols and treatments mitigating transmission represent a major and urgent unmet public health need; this study will rigorously address the *in vivo* utility of widely available oral rinses in limiting SARS-CoV-2 viral infectivity.⁵⁻⁸

Like other enveloped viruses, coronaviruses are surrounded by a lipid bilayer which allows for spike glycoproteins required for infection to be inserted.³ The mouth rinses proposed in this study have shown success in previous studies in disrupting this lipid envelope in other viruses, and there is

promise that they will do the same to the SARS-CoV-2 virus. Effect size: Using data from Meiller *et al.* we calculated power at four time points.¹⁸ Time points included: Post-0 (immediately after rinse), Post-30 (30 min after rinse), and Post-60 (60 min after rinse). In addition, we calculated a Post-45, which was the midpoint between 30 and 60 min in the Meiller *et al.* data. Based on this viral study evaluating mouth rinse efficacy against infectivity of Herpes Simplex Virus, an enveloped virus, power calculations were determined to estimate effect size and determine sample size as a function of length of mouth rinse time course.¹⁸ The sample size was justified by a paired T-test on outcomes between time points. With three simultaneous comparisons (t_1-t_0 , t_2-t_1 , t_3-t_0) over 30 min, an $n=16$ sample size can detect the effect size in Cohen's $d=0.7$, which is between medium and large, with 80% power and 0.016 type-I error rate by Bonferroni correction. Therefore, with four simultaneous comparisons (t_1-t_0 , t_2-t_1 , t_3-t_0 , t_4-t_0) the sample size required for each arm is ~25 participants per group to discern oral rinse efficacy at any given time point.

Subjects will be required to rinse their mouths with an unlabeled/blinded mouthrinse for 30-60 sec. Per the instructions on the product label, it is recommended to rinse for 30-60 sec, depending on the rinse (on-label directions will be followed). The mouthrinses chosen for this study are all commercially available products with known antiviral effects.

The intervention will be administered orally because an oral mouth rinse will be utilized, and the dosage will range from 10 mL to 20 mL, dependent on the dosage instructions on the product label. The duration of the intervention will be 60 min, with collection of pooled saliva samples pre-rinse and every 15 minutes (0 min, 15 min, 30 min, 45 min, and 60 min) post-rinse. This time period was chosen to be similar to that of a typical dental appointment. Multiple saliva samples will be collected to show how long the proposed mouth rinses are successful in deactivating the virus.

Peripheral blood will be collected at the end of salivary collection. Participants will be provided materials and oral hygiene instruction related to daily use of oral hygiene products provided by the study. Participants will be asked to keep a daily diary of oral hygiene performance, product usage, COVID-19 symptoms and exposures. During the week between study visits, participants will be directed to brush with Colgate toothpaste (at least twice per day) and rinse with the Colgate mouthrinse (according to on label instructions). Participants will be scheduled to return to the GoHealth Clinical Research Unit at one week after the first visit, during which additional salivary (1 time point, 2 mL of saliva over 5 min, no antiseptic mouth rinse will occur) and blood samples will be collected (2 - 5 mL in EDTA-containing blood collection tubes). At the conclusion of sample collection, the participant will undergo a periodontal exam. Study participation concludes following the periodontal exam.

Samples will be evaluated at both timepoints for inflammation-related cytokines and chemokines using pre validated quantitative multiplex assays (Luminex technologies), diaries will be reviewed and periodontal charting will be evaluated for differences between patient groups. A periodontal exam will consist of periodontal probing depths (PD), clinical attachment level (CAL) and bleeding on probing (BOP) at six sites for each tooth excluding third molars. Once collected, the periodontal exam data will be evaluated and the periodontal status for each participant will be assigned via the case definitions for periodontitis, gingivitis, and clinical periodontal health as described in the 2017 World Workshop on the Classification of Periodontal and Peri-Implant Diseases and Conditions and the 2012 Centers for Disease Control and Prevention and American Academy of Periodontology case definitions.^{19,20} Patients will be informed of their periodontal status. Patients with any periodontitis or gingivitis diagnosis will be informed of their diagnosis and will be

referred to an oral healthcare provider for further treatment. Patients' final periodontal status will be the tertiary outcome of the periodontal exam and will be reported as the percentage of participants categorized into each diagnostic group. This study involves two on-site 90-minute visits.

Known and potential risks include breach of confidentiality, slight discomfort, and a low chance of a previously undiagnosed allergy. To minimize risk of breach of confidentiality, all patients will be assigned a unique study ID. There will be no other subject identifiers on samples or data. The linkage file that relates patient's names to study ID numbers will be stored on a UNC secure server. All desktops computers and servers are kept in locked facilities and in accordance with UNC IT/security safeguards and policies.

All providers and study researchers have been trained in and abide by HIPAA procedures, and confidential patient information will be stored on secured, encrypted UNC servers. Patients will already have been provided with their SARS-CoV-2 status through their healthcare providers, and this confidential medical information will not be released by any study personnel. Some patients may perceive the mouth rinse as causing some discomfort if they dislike the flavor or the bubbling sensation. A small fraction of patients (rare <1%) may be allergic to the mouth rinse. We will ask detailed questions in our screening protocol if patients are allergic to any component of the mouthrinses, but if a patient answers no to all screening questions regarding allergy and then they are allergic, it may lead to an adverse allergic reaction.

The following table lists adverse effects associated with each mouthrinse proposed in this study:

mouthrinse*	Adverse effects
1.5% w/v hydrogen peroxide rinse (Peroxyl)	
• If irritation persists for 7 days, is severe, is due to orthodontic appliances and/or dentures, or swelling or fever develops, the patient's condition needs to be re-evaluated by a doctor or dentist.• Overdose can injure the gums and continued use of hydrogen peroxide may cause reversible hypertrophy of the papillae of the tongue known as 'black hairy tongue' therefore using this product at high doses or for long periods of time is not recommended.• Some cases of mucosal irritation and swelling of the oral tissues have been reported specially with high doses or in continued use.
0.12% Chlorhexidine Gluconate (Periogard)	
• The most common (1) an increase in staining of teeth and other oral surfaces, (2) an increase in calculus formation, and (3) an alteration in taste perception; see WARNINGS and PRECAUTIONS. Oral irritation and local allergy-type symptoms have been spontaneously reported as side effects associated with use of chlorhexidine gluconate rinse. The following oral mucosal side effects were reported during placebo-controlled adult clinical trials: aphthous ulcer, grossly obvious gingivitis, trauma, ulceration, erythema, desquamation, coated tongue, keratinization, geographic tongue, mucocoele, and short frenum. Each occurred at a frequency of less than 1.0%. Among postmarketing reports, the most frequently reported oral mucosal symptoms associated with chlorhexidine gluconate oral rinse are stomatitis, gingivitis, glossitis, ulcer, dry mouth, hypesthesia, glossal edema, and paresthesia. Minor irritation and superficial desquamation of the oral mucosa have been noted in patients using chlorhexidine gluconate oral rinses. There have been cases of parotid gland swelling and inflammation of the salivary glands (sialadenitis) reported in patients using chlorhexidine gluconate oral rinse.

1:1.5% w/v hydrogen peroxide rinse (Peroxyl) 2 nd : 0.12% Chlorhexidine Gluconate (Periogard)	
 • No additional adverse effects documented from sequential use. • Please see above for adverse effects of each rinse individually. • For the sequential Peroxyl (1st) and Periogard (2nd) rinses, both oral rinses will be conducted in an on label fashion. The patient will begin by rinsing with 10 mL of Peroxyl for 60 seconds and then expectorate the mouthrinse into an empty tube. Then the patient will rinse with 15 mL of Periogard for 30 seconds, and spit this mouthrinse into a separate tube.
0.075% Cetylpyridinium Chloride (Colgate Total Zero)	
 • If more than used for rinsing is accidentally swallowed, get medical help or contact a Poison Control Center right away
Sterile Water	No contraindications

**All mouthrinses are commercially available in the USA, routinely used in clinical settings, and will be used in an on-label manner.*

3. STUDY DESIGN

One of the aims of this placebo-controlled, randomized, double-blinded study is to measure the efficacy of antiseptic mouthwashes on reducing SARS-CoV-2 cellular infectivity in COVID+ patient saliva (described above). Asymptomatic and symptomatic SARS-CoV-2+ subjects will be enrolled in the study (according to Inclusion and Exclusion Criteria - Section A.3). Symptomatic SARS-CoV-2+ subjects will be enrolled within 7 days of symptom onset. Subjects' samples are collected in the GoHealth Clinic (Adams School of Dentistry, UNC Chapel Hill, North Carolina, USA). Asymptomatic SARS-CoV-2+ subjects will be enrolled within one week of likely exposure. Study participants who meet all inclusion criteria without any exclusion criteria will be randomized to either an experimental or control group using block randomization.

Participants give a baseline salivary sample (2 mL over 5 min) and then asked to rinse with an mouth rinse for 30-60 sec (on-label instructions) according to the table below:

mouthrinse*	Number of final participants (sample size)	Group
1.5% w/v hydrogen peroxide rinse (Peroxyl)	25**	Experimental
0.12% Chlorhexidine Gluconate (Periogard)	25	Experimental

1 st Peroxyl; 2 nd Periogard [^]	25	Experimental
0.075% Cetylpyridinium Chloride (Colgate Total Zero)	25	Experimental
Sterile Water	25	Control

**All mouthrinses are commercially available in the USA, routinely used in clinical settings, and will be used in an on-label manner.*

***30 participants will be enrolled per regimen to ensure that complete data will be obtained from at least 25 participants per regimen. We assume that ≤ 5 enrollees will drop out or have incomplete data. 30 participants will be enrolled per arm to collect full data sets from 25 participants per arm, assuming some patients will need to be replaced due to inability to complete a visit (missing data).*

[^]For the sequential Peroxyl (1st) and Periogard (2nd) rinses, both oral rinses will be conducted in an on-label fashion. The patient will begin by rinsing with 10 mL of Peroxyl for 60 sec and then expectorate the mouthrinse into an empty tube. Then the patient will rinse with 15 mL of Periogard for 30 seconds and spit this mouthrinse into another empty tube.

After the participant expectorates the mouth rinse, research staff will collect another salivary sample (T_0 , 2 mL over 5 min). During a 10 min recuperation period, the study participants will answer demographics survey questions and questions regarding the taste, color, flavor and general acceptability of using the mouthrinse as part of routine dental and medical visits. At 15 minutes post-rinse, the participant will be asked to provide an additional saliva sample (2 mL over 5 min), followed by another 10-minute recuperation period. This sequence will be repeated for the 30, 45- and 60-minute time points post-rinse. At 60 minutes, the study participant will give their final salivary sample (2 mL over 5 min).

The samples will be stored and used for determining SARS-CoV-2 viral load by RT-PCR and inflammation-associated cytokine and chemokine concentration (pg/mL). The impact of mouthrinses on viral load in samples will be using a Relative quantification (RQ) ratio. A cycle threshold cut off (see sections 9.4-9.5) of 22 will be used for determining which samples will be used in downstream viral infectivity assays. Viral infectivity will be calculated (see sections 9.4-9.5) and yield a Reduction Factor as quantified output. Peripheral blood will be collected at the end of salivary collection (2 - 5 mL in EDTA-containing blood collection tubes).

Participants will be provided materials and oral hygiene instruction related to daily use of oral hygiene products provided by the study. During the week between study visits, participants will be directed to brush with Colgate toothpaste (at least twice per day) and rinse with the Colgate mouthrinse according to on-label instructions (10-20 mL, 30-60 seconds, 2-3 times per day depending on mouthrinse).

Participants will be asked to keep a daily diary of oral hygiene performance, product usage, COVID-19 symptoms and exposures. Participants will be given a \$30 gift card for their participation in visit 1. Participants will be scheduled to return to the GoHealth Clinical Research Unit at one week after the baseline assessment, during which additional salivary (1 time point, 2 mL

of saliva over 5 min, no rinse will occur) and blood samples (2 - 5 mL in EDTA-containing blood collection tubes) will be collected.

At the conclusion of sample collection, the participant will undergo a periodontal exam and will receive a \$50 gift card for their participation in visit 2. Study participation concludes following the periodontal exam after visit 2.

Missing data may occur due to participants being unable to complete a study visit due to health concerns or insufficient salivary production. Any missing data will be excluded from the study analysis. We do not anticipate that this will bias the data in any way. To accommodate this eventuality, we plan to enroll 30 participants per arm, to be able to have 25 participants per arm with full datasets.

All salivary samples will be collected on ice in sterile 50 mL conical vials and blood will be collected in EDTA-containing blood collection tubes. All collection tubes will be labelled “COVID Core” using pre-printed labels including the participants random alphanumeric study ID. Saliva samples will be cataloged and stored at the UNC Delta COVID Translational Initiative (also referred to as the COVID Core) for future RT-PCR, cytokine and chemokine concentration (Luminex) and viral infectivity assays. Samples will be transported on ice in a secondary container from the collection site to 4403A Koury Hall in leak proof biohazard bags. Samples will be processed according to the **sample processing and outcomes** procedure (below).

Participants who successfully provide salivary and blood samples and follow study protocols will receive a \$30 gift card as compensation at the end of visit 1 and \$50 at the end of visit 2. This study involves two, 90 minute on site visits.

During the period that the study participants are present in the clinic and giving saliva samples, we will monitor patient wellbeing and inquire about their comfort. If participants exhibit signs of distress or if oxygen saturation drops, research study staff will contact emergency medical responders to visit the patient and if deemed appropriate, the participants will be escorted to UNC hospital (adjacent building).

This time course analysis design will allow us to investigate if any of the antiseptic mouthwashes are effective at reducing SARS-CoV-2 in salivary secretions of study participants as well as to determine the therapeutic window if effective. We have designed this study to recapitulate a standard oral exam and procedure time (~1.5 hrs in length). Further, the design will allow for a kinetic analysis of viral shedding in salivary secretions and to identify the most effective mouth rinse.

Sample processing and outcomes

Sample processing: Following collection, saliva samples will be processed according to existing BSL2+ SOP protocols (COVID Core, UNC (PI: [name], [name] and [name]) by pre-authorized personnel. Samples will be assessed for **1**) molecular presence of SARS-CoV-2, **2**) salivary antibody responses to SARS-CoV-2, **3**) in vitro infectibility and **4**) inflammatory biomarkers.

1. Molecular analysis: For molecular analysis, samples will be inactivated by adding 2 mL of TriZol LS reagent to each 500 μ L saliva aliquot (4:1 ratio) and mixed by inversion. These samples will be further aliquoted at 250 μ L in 1.5 mL Eppendorf tubes and stored in an “Inactivated Samples -80 °C Freezer” until further analysis.

2. Antibody responses: an aliquot of saliva will be inactivated in a 56 °C water bath for 30 min. 250 µL aliquots will be transferred into 1.5 mL cryovials and stored in the “Inactivated Samples -80 °C Freezer” in 4403A Koury Hall until further analysis.

3. In vitro infectivity: Samples will be stored in the “Activated Samples -80 °C Freezer” in 4403A Koury Hall until further analysis.

At analysis, all samples will be serially diluted in sterile PBS (10⁻¹⁰-fold dilutions). Plaque assays will be performed using Vero E6 cells at confluence in 96-well cell culture plates. Briefly, cell cultures will be washed with sterile PBS and samples containing virus will then be plated in duplicate (100 µL per well). Plates will be incubated at 37 °C for 45 min with occasional rocking. Then 2 mL of 0.5% agarose in minimal essential media (MEM) containing 2% FBS and antibiotics will be added per well. Plates will be incubated at 37 °C for 72 hours, fixed with 10% buffered formalin, followed by the removal of the overlay, and then stained with 0.2% crystal violet to visualize plaque forming units (PFU). Average PFU will be evaluated by OD. All assays will be performed in BSL-3 laboratory setting. (PMID: 32475066)

Unprocessed saliva exceeding immediate experimental capacity will be stored in aliquots of 250 µL volume in 1.5 mL Eppendorf tubes and stored in “Activated Samples -80C Freezer.”

Survey data: The survey data will be analyzed and used to identify clinical and other factors impacting applicability of each of the mouth rinses.

4. Detection of Inflammatory biomarkers: Inflammation-associated cytokine and chemokine concentrations (IL-6, CXCL-10, IL-8, and IL-10 [pg/mL]) will be quantified from saliva and blood samples using multiplex analyte analysis (Luminex technology) and using internal, manufacturer supplied standards of known concentration (pg/mL). These analyses will be performed by the DELTA Translational Core according to COVID Core SOP (PI: [name] and [name]). The COVID Core staff routinely performs these analyses on samples from SARS-CoV-2+ research study participant samples.

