If a patient suffers from xerostomia/dry mouth, such that s/he cannot produce the baseline salivary sample volume or the immediate, 15 minute and 30 minute post-rinse saliva volumes, s/he will be removed from the study with a parking voucher, but without a visit 1 \$30 gift card and will be replaced. This would lead to missing data at the uncompleted time points. If a patient suffers from dry mouth, such that s/he cannot produce salivary sample volumes needed for later time points (45 min or 60 min post-rinse) but s/he produced sufficient baseline, immediate, 15 min and 30 min post-rinse samples, the participant will still be compensated with the visit 1 \$30 gift card and parking vouchers, and will remain in the study for visit 2 participation, if willing. At the conclusion of the visit 2 on site appointment (after saliva and blood samples have been collected and the periodontal exam is completed), participants will receive a \$50 gift card and parking vouchers. If a participant fails to carry out the at-home oral hygiene regimen with diary, cannot provide salivary or blood samples at visit 2, or cannot undergo the oral exam, they will not be provided the \$50 gift card for visit 2. Missing or deficient samples will be noted in CDART.

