11.3.3 Metrics

Every salivary sample will be collected in a conical tube with millimeter markings to monitor salivary volume. If insufficient saliva is collected, the study personnel collecting the samples from participants will note insufficient volume in the CDART database for each applicable time point and will indicate in CDART if the subject must be withdrawn and replaced. If a patient is unable to generate sufficient saliva for the 0 min, 15 min or 30 min post-rinse time points, the subject will be removed from the study and this will be noted in CDART along with their insufficient samples. If a subject is unable to generate sufficient saliva for time points 45 or 60 min post-rinse, the participant will remain in the study but their insufficient samples will be noted in CDART. If a patient is unable to tolerate the blood draws or periodontal exam, this will be noted in CDART and the patient will be withdrawn from the study.

For RT-PCR, viral infectivity and multiplex Luminex assays, all salivary samples will be run in triplicate with standard experimental controls (negative and positive) and protocol quality checks performed by research technical personnel in the COVID Core, [name], [name] and [name] laboratories. SARS-CoV-2 viral infectivity and RNA level will be measured using an *in vitro* infectivity assay (Reduction factor [RF] calculated from PFU / mL) and RT-PCR (relative quantification [RQ] ratio). Cytokine and chemokine concentration (pg/mL) will be measured using a prevalidated multiplexed quantitative analyte assay on a bioanalyzer (Luminex technologies). This objective provides urgently needed data to guide healthcare workers on the proper use of specific commercially available mouthwashes capable of reducing SARS-CoV-2 viral infectivity and potentially limiting COVID-19+ transmission.

Outcome assessments will be conducted weeks to months after the study visit, when RT-PCR, viral infectivity and cytokine/chemokine assays are conducted in the COVID Core and the laboratory of [name].

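### Removing participants for an undefined saliva shortfall at baseline, 0, 15 or 30 minutes can lose randomised participants whose samples would suffice for both primary assays

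*Combined protocol and SAP*

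**What the plan says.** **Volume.** Section 3 opens visit 1 with "Participants give a baseline salivary sample (2 mL over 5 min") and asks for the same amount after the rinse: "the participant will be asked to provide an additional saliva sample (2 mL over 5 min), followed by another 10-minute recuperation period". The Précis and sections 5.1 and 6.2 also state 2 mL. No other sample volume appears.

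**Removal.** Section 6.2.5, repeated in section 9, says that if a patient with dry mouth "cannot produce the baseline salivary sample volume or the immediate, 15 minute and 30 minute post-rinse saliva volumes, s/he will be removed" from the study, and then replaced. Section 11.3.3 words it differently: "If a patient is unable to generate sufficient saliva for the 0 min, 15 min or 30 min post-rinse time points", the subject is removed. For 45 or 60 minutes, section 11.3.3 says "the participant will remain in the study but their insufficient samples will be noted in CDART". None of these sections gives a figure for a sufficient volume.

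**Use of the saliva.** Under sample processing in section 3, for RNA, "samples will be inactivated by adding 2 mL of TriZol LS reagent to each 500" µL aliquot. For the plaque assay, "samples containing virus will then be plated in duplicate (100" µL per well). Section 11.3.3 says triplicate for RT-PCR, infectivity and Luminex. The same sample also supplies a salivary antibody assay (250 µL aliquots), Luminex cytokines (volume not stated) and stored surplus (250 µL aliquots).

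**Consequences.** Section 3 plans 30 enrolled per arm to obtain 25 with full data. It names low saliva production as a cause of missing data, excludes missing data from the analysis, and expects no bias.

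**The concern.** The rule decides whether a participant stays in the trial, yet it is not tied to what the primary outcome needs. Three of its four trigger collections come after randomisation and after the rinse. Someone who gives, say, 1.3 mL at 15 minutes could be removed although both viral load and infectivity could be measured on that sample, and the 30-minute sample would then never be taken. The primary hypothesis concerns persistence to 30 minutes, and section 10.4 runs infectivity at baseline and 30 minutes only, so the rule can forfeit the sample that matters most because of one that section 10.4 does not use for infectivity.

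Removing and replacing participants after they have rinsed also departs from the comparison of the groups as randomised. The statement that this cannot bias the data has no support in the documents. Section 4.2 excludes severe xerostomia and Sjögren's syndrome, so people with ordinary lower flow can still be randomised.

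**Working it through.** **1. The plan's allowance.** Up to 5 losses in 30 is 16.7%, and 25 / (1 − 5/30) = 30, so the planned 30 per arm reproduces. Five arms of 30 make 150, whereas the Précis and section 10.4 give 125; I use 30 per arm, as section 3 does.

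**2. Saliva needed for the two primary assays**, from section 3 and section 11.3.3:

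| Reading | RNA | Infectivity | Total |
|---|---|---|---|
| Duplicate wells | 0.5 mL | 2 × 0.1 = 0.2 mL | 0.7 mL |
| Triplicate wells | 0.5 mL | 3 × 0.1 = 0.3 mL | 0.8 mL |
| Infectivity in whole storage aliquots | 0.5 mL | 2 × 0.25 = 0.5 mL | 1.0 mL |

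This is 35% to 50% of 2 mL. Over 5 minutes, 2 mL is 0.4 mL/min, while 0.7 to 1.0 mL is 0.14 to 0.20 mL/min. The number of RNA aliquots per sample is not stated. If triplicate RT-PCR meant three separate 0.5 mL aliquots, the total would be 1.5 + 0.3 = 1.8 mL. One aliquot can supply triplicate runs, however: 0.5 mL saliva plus 2 mL reagent is 2.5 mL, which fills ten 0.25 mL tubes.

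**3. Which shortfalls remove a participant.**

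| Collection | Sections 6.2.5 and 9 | Section 11.3.3 |
|---|---|---|
| Baseline | Removed | Not mentioned |
| 0, 15, 30 min | Removed (joined by *and*) | Removed (joined by *or*) |
| 45, 60 min | Stays in | Stays in |

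Taken together, the natural reading is that a shortfall at any one of four collections is enough.

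**4. Possible loss per arm.** The shortfall probability per collection, p, is not in the documents, so the values below are assumptions. If the four collections are independent, loss = 1 − (1 − p)^4. If the same people fall short every time, loss = p. The last column of each case is the binomial probability that at least 25 of 30 remain, with no other losses.

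| p | Independent: loss | Of 30 | P(≥25 remain) | Same people: of 30 | P(≥25 remain) |
|---|---|---|---|---|---|
| 2% | 7.8% | 2.3 | 0.97 | 0.6 | 1.00 |
| 5% | 18.5% | 5.6 | 0.51 | 1.5 | 0.997 |
| 10% | 34.4% | 10.3 | 0.03 | 3.0 | 0.93 |

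The expected loss equals the whole allowance at p = 1 − (5/6)^(1/4) = 4.5% under independence, and at p = 5/30 = 16.7% if the same people always fall short. The allowance must also cover every other cause of incomplete data.

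**The case against.** The strongest reply is that the protocol only asks for 2 mL and nowhere makes it a pass/fail limit. The removal text speaks of dry mouth and of sufficient saliva without a number, and sections 6.2.5 and 9 also list low saliva production among reasons for which the investigator may discontinue a subject. That stands: a reader might infer a hard 2 mL cut-off, and the documents do not state one. But 2 mL is the only figure staff have when they read a marked tube, and if a lower threshold was meant, it has to be written down.

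A reader might also infer that half of each sample is surplus. The documents do not show that. Salivary cytokines are a secondary outcome with a hypothesis (section 10.5.2), measured across the time course (section 10.6), and their volume is not given. Only the antibody assay has no outcome or analysis in section 10. The figure of 0.7 to 1.0 mL is derived, and it leaves out handling losses and repeat runs.

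Nor do the documents support a claim that the rule will exhaust the allowance. Low flow is largely a personal trait, so shortfalls are likely to cluster in the same people, and removed participants are replaced. A claim that the rule biases the comparison between arms goes too far as well. Dry mouth appears among postmarketing reports for chlorhexidine (adverse-effect tables in sections 2.2 and 8), which two of the five arms use, but with no rate and no link to a single rinse within 30 minutes. A baseline shortfall precedes the rinse and cannot be caused by it.

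Finally, section 6.2.5 says data are missing at the uncompleted time points, so it is unclear whether samples already given by a removed participant are discarded. Removal does, however, prevent every later sample.

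**Conclusion.** The point holds in a limited form. The protocol removes participants, mostly after randomisation, on a volume criterion that it does not define and does not relate to the primary assays. On its own volumes those assays need about 35% to 50% of the stated 2 mL, provided one RNA aliquot per sample is enough. The rule is also stricter than the design requires: partial data are already accepted at 45 and 60 minutes, and neither the time-point ANCOVA nor the repeated-measures model needs every post-rinse sample.

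The number of participants lost cannot be obtained from the documents. It ranges from well inside the allowance of 5 in 30 to well beyond it, depending on an assumed shortfall rate and on how strongly shortfalls cluster within people. Differential loss between arms remains possible but not shown, which is enough to make the no-bias statement in section 3 unsupported.

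**What to change.** - Keep 2 mL as the collection target. Define an insufficient sample as one below a laboratory-confirmed minimum for RT-PCR plus the plaque assay; the protocol's volumes suggest 0.7 to 1.0 mL.
- Fix the order of use: RNA, infectivity, cytokines, antibody. RNA comes first because sections 3 and 10.4 admit a sample to the infectivity assay only at a cycle threshold of 22 or lower.
- Treat a short sample as missing only for the assays and time points that it cannot supply.
- Do not remove or replace randomised participants for a post-rinse shortfall. Continue their later collections, analyse the samples they give, and report shortfalls by arm and time point.
- Reconcile sections 6.2.5, 9 and 11.3.3 on which collections count and whether one shortfall is enough, and reconcile duplicate with triplicate plating.
- Delete the no-bias statement in section 3.

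The cost is protocol wording, an aliquoting instruction and a laboratory check of the minimum. The downside is some missing cytokine or antibody values, and less stored surplus, at short-volume time points.
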